1. PURPOSE OF THE STUDY AND BACKGROUND

1.1: Purpose of the Study:

Inactivated influenza vaccine (“IIV”) is an intramuscular vaccine administered to children ≥ 6 months in age that is composed of highly purified HA and NA surface glycoproteins and contains trace, if any, activators of the immune system. In contrast, live attenuated vaccine (“LAIV”) consists of intranasally delivered, attenuated viruses that stimulate the innate immune system while undergoing limited viral replication in the upper respiratory tract. Some children also continue to first encounter influenza through natural infection, where high levels of viral replication stimulate vigorous innate immunity. Although CD4 T cells play a key role in regulating the influenza-specific B cell, CD8 T cell, and innate immune responses, little is known about the immediate and long-term effects these different routes of early childhood priming have on CD4 T cell mediated immunity. The long-term goal of this research is to understand how a child’s early exposure to influenza shapes immunity and poises the immune system to respond to subsequent influenza challenge. Our objective is to determine how the anti-influenza CD4 T cell and antibody responses are altered by the mode of primary influenza encounter and establish the consequences this has on subsequent influenza vaccination. To accomplish this objective, we will enroll two cohorts of young children: 1) a cohort of 24 through 35 month of children administered either LAIV or IIV and 2) a separate cohort of infants first exposed to influenza through prime-boost administration of IIV or natural infection during their initial influenza season. All enrolled subjects will be followed longitudinally to the subsequent influenza season and then rechallenged with IIV. These cohorts of children will allow us to test the following hypotheses:

- 1) Compared to intramuscular IIV, initial exposure to intranasal LAIV establishes a greater and more polyfunctional CD4 T cell response in children 24 through 35 months of age
- 2) Compared to a first exposure to influenza through infection, primary infant vaccination with IIV establishes a more limited CD4 T cell repertoire that consists predominately of IL-2 producing cells, and
- 3) The CD4 T cell responses established with this initial priming will differentially poise subjects to respond to revaccination with IIV the following influenza season

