Figure 2: Expansion of CD4 T cells directed against conserved peptides is seen following pandemic H1N1 vaccination, with a correlation between the development of an HA-specific CD4 T cell response and neutralizing antibody titer. Subjects received the monovalent inactivated subvirion A/California/07/09 vaccine and CD4 T cell responses against conserved and nonconserved peptide pools were examined by IFN γ Elispot assay using CD8 and CD56 depleted PBMCs. While a response to HA (A) and NP/M1 (B) peptide pools expected to be conserved compared to recently circulating H1N1 strains was detected, little response to peptides expected to be unique to this virus was seen in subjects without prior immunity (C). Error bars represent the standard error of the mean and P-values calculated using Wilcoxon signed rank test. Development of a CD4 T cell response was correlated with the maximum microneutralization titer achieved (D). R- and p-values determined using the Spearman correlation coefficient.

- To evaluate in an unbiased way the influence of previous influenza exposure on PBMC gene expression patterns using RNA-seq analysis
- To assess the mucosal immunity established by these modes of priming and determine whether any initially established differences in mucosal immunity are maintained on subsequent rechallenge with IIV

To accomplish these objectives, we plan to enroll a cohort of 60 children who have previously been vaccinated with at least 2 doses of IIV and who are between the ages of 24 and 35 months into cohort 1. These children will be block randomized to receive either LAIV (n=30) or IIV (n=30) in groups of 5 unless a history of isolated wheezing in the past year is present. As LAIV is not indicated in children with a history of recent wheezing, otherwise eligible children who have a history of wheezing will be defaulted to receive IIV. Children will have a blood draw and nasal wash on study entry and again at days 10 (+ 4 days/- 2 days) and 24 (+/- 4 days) post vaccination. They will then be followed through to the subsequent influenza season, when they will be rechallenged with IIV with blood draws and nasal washes pre-vaccination and again at days 10 (+ 4 days/- 2 days) and 24 (+/- 4 days) post vaccination (Figure 3).

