The age range of the first cohort of children was chosen because children first become eligible to receive LAIV at the age of 24 months. Thus, the age range of 24 through 35 months will capture children receiving LAIV for the first time. A block randomization scheme will be used as there is a large population of children with a past history of isolated wheezing as a result of viral illnesses such as bronchiolitis that have been shown to respond

equivalently to influenza vaccine (59, 74, 75). We feel that including this population of children in the study will improve recruitment and allow for broader applicability of our study results, but as these subjects are not eligible to receive LAIV (17, 18), their inclusion also precludes a completely blinded randomization scheme. With block randomization, eligible subjects will be enrolled to receive either LAIV or IIV in groups of 5 unless a history of isolated wheezing in the past year is present, in which case they will be defaulted to receive IIV as long as no other exclusion criteria are present.

The age range of the second cohort was chosen to enroll infants in their first influenza season with no history of prior exposure to influenza virus. Thus, this cohort will allow examination of the true primary response to influenza infection or inactivated vaccination. Children between 6 and 12 months of age who have not previously had an influenza infection or vaccination will be eligible to participate in the vaccination group. All of these children will receive IIV, as LAIV is not approved for children this age. This cohort will receive a prime-boost vaccination series, with vaccine doses separated by 28 (+ 14) days as recommended by the AAP and ACIP (17, 18). To minimize blood draws, we will only interrogate the immune response following the second vaccine dose. Children between 3 and 12 months of age who present with an influenza-like illness and have no previous history of influenza vaccination will be eligible to participate in the infection group. Study personnel will obtain nasal swabs from potential subjects for a rapid influenza antigen test on illness presentation (typically this occurs at day 3-4 post illness onset). If positive, they will be eligible for further study participation. Influenza real-time RT-PCR will be used to confirm rapid antigen test results, however these results will not be available in time to influence subject enrollment.

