d. Vulnerable Subjects: As the goal of this study is the study of the early immune response to childhood influenza infection and vaccination, by definition it needs to include children, who are a vulnerable population. To safeguard rights and welfare of these children, the parents or legal guardians of all subjects recruited into this study will provide written informed consent. Since the subjects involved will all be less than 3 years of age, it will not be possible to obtain subject assent, although study procedures will be explained to all subjects as developmentally appropriate based on the subject's age. To maintain subject privacy, paper copies of subject PHI will be stored in a locked file cabinet within a locked office, with an electronic extraction of this data maintained on a password protected and secured university computer.

All blood will be drawn by experienced and trained pediatric nurses, with pain minimized through comforting and distraction techniques. Only the minimum amount of blood necessary to achieve the study objectives will be obtained, with the blood volume being within a level accepted as safe (Table 1). As a child's total blood volume is related to body weight, we have chosen a weight based approach to determine the volume of blood to be obtained. This will allow us to optimize our likelihood of being able to accomplish the study objectives while still prioritizing the safety of the child. Current policy suggests that blood volume limits between 1% and 5% of the total blood volume on a single draw and up to 10% of total blood volume over an 8 week period will present minimal risk to children (76). A child's total blood volume estimated at around 80 mL/kg. The proposed blood draws in this protocol impose a maximum upper limit of 1 mL/kg on any single draw (about 1.25% of estimated TBV), with a maximum of 3 mL/kg (about 3.75% of estimated TBV) over any 8 week period for all pediatric patients. This volume remains well below the upper limit of 10% of total blood volume in an 8 week period and is consistent with the available evidence on what will present minimal risk to children while still providing enough PBMCs to perform the in depth analysis of CD4 T cell specificity and functional capacity and antibody responses required for this study.

3.2: Inclusion and Exclusion Criteria

a. Inclusion Criteria:

- Age

- Between 24 and 35 months for cohort 1

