- Between 6 and 12 months to participate in the vaccination arm of cohort 2 (cohort 2A)
- Between 3 and 12 months to participate in the natural infection arm of cohort 2 (cohort 2B)
- Gestational age of ≥ 37 weeks at birth
- Parent/guardian can provide informed consent
- Available for the duration of the study
- History of previous IIV administration **ONLY** for participation in cohort 1
- Acute illness documented to be due to influenza virus **ONLY** for participation in the natural infection arm of cohort 2 (cohort 2B)

b. Exclusion Criteria:

- Immunosuppression as a result of an underlying illness or condition (including HIV or a primary immunodeficiency syndrome)
- Active neoplastic disease
- Use of potentially immunosuppressive medications currently or within the past year (including chemotherapeutic agents) or chronic (>2 weeks) use of oral or inhaled steroid therapy
- A diagnosis of asthma requiring chronic controller medication
- Previous administration of influenza vaccine in the current influenza season
- Receipt of immunoglobulin or another blood product within the year prior to study enrollment
- An acute illness within the previous 3 days or temperature $>38^{\circ}$ on screening **EXCEPT** for participation in the natural infection arm of cohort 2 (cohort 2B)
- A contraindication to influenza vaccination **EXCEPT** infants between 3 and 5 months presenting with natural influenza infection whose only contraindication is their current age

3.3: Discussion of Subject Population:

The main objective of this Study is to evaluate the specificity and functional potential of the CD4 T cell response and the quantity, breadth and avidity of the neutralizing antibody response following influenza infection or vaccination. In order to eliminate potential confounding factors, we plan to exclude any subject who has an acute or chronic medical condition that may result in immunosuppression. Also excluded will be potential subjects that have recently received immunosuppressive medications or blood products that could potentially interfere with vaccine immunogenicity. This exclusion will include children with a history of asthma who require chronic controller medicines, including inhaled steroids. Children with only a history isolated wheezing not on chronic controller therapy will be allowed to participate, although they will not be administered LAIV.

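### Age 24-35 months does not by itself make cohort 1 LAIV-naive, and no eligibility criterion excludes LAIV given in an earlier season

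*Combined protocol and SAP*

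**What the plan says.** Hypothesis 1 in section 1.1 is that, compared with IIV, "initial exposure to intranasal LAIV establishes a greater and more polyfunctional CD4 T cell response in children 24 through 35 months of age". The exposure of interest is thus a first exposure to LAIV.

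Section 2.2 gives the reason for the age window: "children first become eligible to receive LAIV at the age of 24 months". From this it concludes that "the age range of 24 through 35 months will capture children receiving LAIV for the first time".

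The cohort 1 conditions that bear on vaccine history are:

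- Age (3.2): "Between 24 and 35 months for cohort 1".
- Prior IIV (3.2): "History of previous IIV administration", marked as applying to cohort 1 only.
- Prior IIV (2.1, repeated in 8.3): "60 children who have previously been vaccinated with at least 2 doses of IIV".
- Exclusion (3.2): "Previous administration of influenza vaccine in the current influenza season".

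No section requires that a cohort 1 child has never had LAIV. Section 13.2 plans no adjustment for prior LAIV and no analysis by it.

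**The concern.** The step from age to first LAIV would hold only if no child in the window could have reached 24 months before the current season. A window of 12 months does not guarantee that, and the eligibility list does not supply the missing condition.

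What is at stake is the definition of the exposure. A child in the IIV arm who had LAIV last season is already LAIV-primed. A child in the LAIV arm who had it last season is not a first-time recipient. Either way the Aim 1 comparison is no longer purely first LAIV against IIV, and Aim 3 carries the same labels into the revaccination year. The protocol itself treats earlier exposure as important: section 1.2 argues that previous influenza exposures shape later responses, and section 5.5 plans analyses with and without children who appear to have had an undocumented infection. Prior LAIV is the same kind of unplanned priming, but has no such safeguard.

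**Working it through.** **Step 1. Can an eligible child have had LAIV last season?** Take a child aged 35 months in October of the enrolment year.

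- Two Octobers earlier: 35 - 24 = 11 months old, so old enough for two IIV doses that season.
- One October earlier: 35 - 12 = 23 months old. The child turned 24 months in November and was age-eligible for LAIV for the rest of that season.
- At enrolment: within the age window, with two prior IIV doses and no vaccine this season.

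This child meets every cohort 1 vaccine-history condition, including the stricter two-dose rule, and may have had LAIV.

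**Step 2. Does the word ONLY in the IIV criterion close the gap?** No. In the 3.2 inclusion list it limits that bullet to cohort 1, just as the same word limits the next bullet to cohort 2B. It does not mean IIV and nothing else.

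**Step 3. Which ages are affected?** Lowest affected age = 24 + months from the last LAIV date of the prior season to enrolment. The documents give neither the cohort 1 enrolment month nor last-season LAIV dates. With October enrolment and an even spread over the 12 months of age (both assumed):

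| Last LAIV in prior season | Lowest affected age | Bands age-eligible |
|---|---|---|
| December | 24 + 10 = 34 months | 2/12 = 17% |
| January | 24 + 9 = 33 months | 3/12 = 25% |
| March | 24 + 7 = 31 months | 5/12 = 42% |
| April | 24 + 6 = 30 months | 6/12 = 50% |

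For enrolment from September to December and a last dose from December to April, the lowest affected age runs from 29 months (September, April) to 36 months, which means none (December, December).

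These are shares age-eligible, not shares vaccinated. An affected child must also have had no IIV that autumn, or have had LAIV as a later dose.

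**Step 4. Reproduce the plan's power.** Section 13.1 gives a difference of 0.3 and an SD of 0.4 on the log10 scale, 30 per arm and a two-sample t-test. No alpha is stated for the table; two-sided 0.05 is assumed.

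- Noncentrality = 0.3 / (0.4 × √(1/30 + 1/30)) = 0.3 / 0.1033 = 2.90, with 58 degrees of freedom.
- Power = 0.815, as stated. All 18 cells of the table reproduce to three decimals. A one-sided test would give 0.890 and does not match.

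**Step 5. Illustrate the effect of a share f with prior LAIV.** The documents do not give f. Worst case, with no contrast in such children: difference = 0.3 × (1 - f). If their contrast is halved: difference = 0.3 × (1 - f/2).

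| f | Difference, worst case | Power | Difference, halved | Power |
|---|---|---|---|---|
| 0 | 0.300 | 0.815 | 0.300 | 0.815 |
| 2% | 0.294 | 0.799 | 0.297 | 0.807 |
| 5% | 0.285 | 0.774 | 0.2925 | 0.795 |
| 10% | 0.270 | 0.729 | 0.285 | 0.774 |

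A share of 5% would arise, for example, from 50% age-eligible × 10% uptake. The 10% uptake is an assumption made only for illustration.

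**The case against.** The strongest reply is that nothing shows any enrolled child had prior LAIV. These are children with an IIV history, only the older part of the window was eligible, and eligibility late in a season rarely leads to a dose. Visit 1 takes a complete medical history, and baseline blood measures influenza immunity at entry. Among the randomised children, prior LAIV would fall in both arms by chance, and such children still receive different vaccines by arm, so the direction of any effect is not established. The planning difference of 0.3 comes from 5-9 year olds, whom section 13.1 does not describe as LAIV-naive, so setting it to zero in prior-LAIV children is a modelling choice.

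Most of this stands, and it limits the size of the point. It does not repair the inference in 2.2. A history taken at visit 1 excludes nobody unless a criterion tells staff what to exclude, and balance between arms does not make the comparison one of first LAIV.

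A reader might also infer that the infant cohort has the same hole, because 3.2 bars only same-season vaccine there too. The documents do not support that as a substantive gap. For the infants given vaccine, section 2.2 states that "Children between 6 and 12 months of age who have not previously had an influenza infection or vaccination will be eligible to participate"; sections 2.1, 2.2 and 8.3 also require the infection group to be unvaccinated. IIV starts at 6 months, and a 12-month-old enrolled in October reached 6 months only in April, so prior-season vaccination is confined to the very top of the age range. The two-dose IIV rule for cohort 1 is likewise already stated in 2.1 and 8.3.

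**Conclusion.** The point holds as a gap in the exposure definition: the statement in 2.2 does not follow from age, and the criteria as written can admit LAIV-experienced children to a contrast defined as initial LAIV exposure. The contrast could be affected; the documents do not show that it is.

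Three stronger readings should be resisted.

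- That everyone over 30 months is affected. That threshold needs October enrolment and LAIV given until April; with a December last dose it is 34 months.
- That Aim 1 power collapses. A 30% share would give 0.516 in the worst case, but it is impossible with a January last dose (25% age-eligible) and needs 60% uptake with an April one (30/50).
- That the contrast must shrink. Its direction is not established.

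On the illustrative shares of 2% to 10%, power lies between 0.729 and 0.807 depending on the share and on how far the contrast is weakened. The plan's 0.815 is correct on its own inputs, but leaves little margin.

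**What to change.** Add to section 3.2, for cohort 1, an exclusion of any previous LAIV in any season, confirmed from the vaccine record at screening. If 30 per arm are still recruited, planned power stays at 0.815.

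If children are already enrolled, record prior LAIV for each and repeat the Aim 1 and Aim 3 comparisons without those who had it, in the way section 5.5 already does for undocumented infection. For scale, 27 per arm at the planned difference of 0.3 gives power of 0.772.

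The cost is one line of protocol text, a record check and slightly narrower recruitment among the oldest cohort 1 children.

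As a minor consistency edit only, align 3.2 with the vaccine-history rules already in 2.1, 2.2 and 8.3.

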negative-sense RNA that encode viral proteins (2). Vaccines against this virus have traditionally relied on inducing antibodies that protect against viral infection by binding to the HA surface glycoprotein and neutralizing virions. However, the rapid accumulation of point mutations in both the HA and NA proteins allow this virus to drift and escape neutralization, resulting in yearly epidemics despite the availability of influenza vaccines (1, 3). In addition, the segmented genome of influenza virus allows sporadic reassortment to occur, which can result in antigenic shift and creation of a strain against which the population has little preexisting immunity. Such a reassortment event occurred in 2009, when a novel swine-origin influenza virus emerged and spread globally, resulting in the first influenza pandemic of the 21st century (4, 5).

It is estimated that 20% of children become infected with influenza yearly, with increasing rates during severe epidemics (6, 7). In addition to providing a reservoir for community infection, childhood influenza infection results in a substantial number of outpatient and emergency room visits and can be associated with significant morbidity, including viral or secondary bacterial pneumonia (6-8). Hospitalization is highest in the very young (estimated at 4.5 per 1000 children 0 to 5 months old) (8), with overall childhood influenza-related mortality estimated at 0.21 deaths per 100,000 children (9). While annual influenza immunization is the most effective method to prevent infection, the influenza vaccine is suboptimal in children (10-12). Some evidence suggests that LAIV may induce broader, more protective immunity in the young (11, 13-16), however recently presented data demonstrated that LAIV failed to protect against H1N1 strains in the 2013-14 influenza season. Further, LAIV is not yet approved for use under the age of 2 due to concerns about the precipitation of wheezing (17, 18). As IIV is universally recommended in the USA beginning at 6 months of age (18, 19), increasing numbers of children are first exposed to influenza via IIV.

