The second cohort of children will be infants between 3 and 12 months of age who will be enrolled to investigate how the primary CD4 T cell response that develops following IIV administration differs from that established after natural influenza infection. Infants who receive vaccine in this cohort will be at least 6 months of age and will be enrolled in the fall before influenza begins to circulate in the community. Infants between 3 and 12 months of age who contract a natural influenza infection before any doses of vaccine are administered will be eligible for the natural infection arm of this cohort. Both of these infant groups will have blood drawn and a nasal wash obtained on study entry and at days 10 (+ 4d/- 2d) and 24 (+/- 4d) post-vaccination and then will be followed to the subsequent influenza season and rechallenged with IIV, with blood draws and nasal washes again completed pre-vaccination and at days 10 (+ 4d/- 2d) and 24 (+/- 4d) post-vaccination (Figure 3). Children who test positive for influenza will be allowed treatment with oseltamivir as recommended by the CDC (73). To accomplish this, the rapid influenza test result will be provided to the child's pediatrician, who will then coordinate treatment of the child.

Figure 3

[figure not shown]

Figure 3: Experimental schematic to determine whether the method of initial priming differentially poises subjects to respond to future influenza encounters. Subjects that receive LAIV, IIV, or that are naturally infected with influenza will have CD4 T cell and antibody responses examined at enrollment and at days 10 and 24 post vaccination. Cohort 1 contains children approximately 24-36 months of age. Cohort 2A contains infants 6-12 months of age in their first influenza season, while cohort 2B contains infants 3-12 months of age. All enrolled subjects will be followed longitudinally for a year and then will be revaccinated with IIV. CD4 T cell responses, antibody response, and transcriptional profiles will be examined prior to revaccination and at days 10 and 24 post vaccination.

2.2: Rationale for Study Design:

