3. CHARACTERISTICS OF THE RESEARCH POPULATION

3.1: Subject Characteristics

a. Number of Subjects: It is anticipated that this study will enroll a total of approximately 180 subjects. This includes 60 children between the ages of 24 and 35 months in the first cohort. These children will be divided equally into two groups of 30, with one group receiving IIV and the other receiving LAIV as described above. We expect to screen up to 120 subjects into the second cohort, of whom 45 will be enrolled in the full study and evaluable. This will include 30 children between the ages of 6 months and 1 year that will receive IIV and 15 children between the ages of 3 months and 1 year who become naturally infected with influenza virus. However, in order to enroll these 15 naturally infected children, we anticipate having to screen up to 90 children with signs of influenza like illness during the height of seasonal influenza circulation, as only a small number of these children will have respiratory infections as a result of influenza virus infection.

b. Gender and Age of Subjects: It is anticipated that there will be an approximately equal distribution of males and females enrolled. This will include 60 children between the ages of 24 and 35 months in the first cohort and up to 120 children between the ages of 3 months and 1 year in the second cohort, of whom 45 will be evaluable.

c. Racial and Ethnic Origin: It is anticipated that the demographic distribution of enrollment will approximately resemble that of the City of Rochester, which is about 40% Caucasian, 40% African-American, 15% Hispanic, and 5% other. No subject will be excluded because of their racial or ethnic origin.

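### A 6-12 month age range with fall enrolment does not by itself put cohort 2A in its first influenza season, and the plan has no rule for infection before entry

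*Combined protocol and SAP*

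**What the plan says.** Section 2.2 (Rationale for Study Design) states that the second cohort's age range was "chosen to enroll infants in their first influenza season with no history of prior exposure to influenza virus", and concludes that the cohort will show the true primary response. The Figure 3 legend in section 2.1 says: "Cohort 2A contains infants 6-12 months of age in their first influenza season".

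Section 2.1 adds that vaccinated infants in this cohort will be at least 6 months old and "will be enrolled in the fall before influenza begins to circulate in the community". Naturally infected infants (2B) are 3-12 months old. Under section 3.1 they are found by screening "during the height of seasonal influenza circulation".

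On earlier exposure, the plan says four things:
- Section 2.2 admits to 2A only infants with no previous influenza infection or vaccination. For 2B it asks only for no previous vaccination.
- Section 3.2 has no criterion on previous influenza infection for either arm. Its vaccine-exposure exclusion reads "Previous administration of influenza vaccine in the current influenza season".
- Section 2.2 says the enrolment blood draw will evaluate influenza-specific immunity at entry. No rule follows from the result.
- Section 5.5 plans analyses with and without subjects who appear to have had an undocumented infection, but only between the last year 1 visit and the first year 2 visit.

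**The concern.** An infant aged 6-12 months in the fall was born between the previous fall and the spring, so it has usually lived through some of the previous influenza season. The age range therefore does not deliver the property claimed for it. An infant infected in mid-winter at 3-12 months is less likely to have been alive in the season before, so the two arms are unequal on this point.

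Hypothesis 2 contrasts priming by infection with priming by IIV. A 2A infant with an unrecognised earlier infection was primed by infection and then vaccinated, and so is misclassified on the exposure under study. This touches the Aim 2 comparison and the 2A v 2B contrast in Aim 3. If such infants respond like the infection arm, the difference between arms shrinks.

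**Working it through.** **1. The plan's own figure.** Section 13.1 gives power 0.871 for Aim 2 with 30 v 15 infants, a difference of 0.4 and SD 0.4 (log10). Using a two-sample t-test at two-sided 5% (the level is not stated for the table, but it reproduces it):

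- Noncentrality = 0.40 / (0.4 × √(1/30 + 1/15)) = 0.40 / 0.1265 = 3.162, with 43 degrees of freedom.
- Power = 0.871, as stated.

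**2. Overlap with the previous season.** The inputs from the documents are the ages (2A 6-12 months, 2B 3-12 months) and the time of entry (fall before circulation; height of the season). The assumptions are mine: ages uniform over the range; previous season Dec-Mar, Dec-Apr, Nov-Apr or Oct-May; 2A entry 1 September to 1 December; 2B entry 1 January to 15 March.

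Three cases by hand, with a Dec-Mar season:
- 2A, entry 1 October: births run from the previous 1 October to 1 April, so practically all infants overlap. One third were born before December (share lived 1) and two thirds during the season (mean share 0.5). Mean share = 1/3 + 2/3 × 0.5 = 0.67.
- 2A, entry 1 December: births run from 1 December to 1 June. Four of six months fall in the season: 67% overlap (66% counting days), mean share 4/6 × 0.5 = 0.33.
- 2B, entry 1 February: births run from 1 February to 1 November. Two of nine months fall in the season: 22% overlap, mean share 2/9 × 0.25 = 0.056 (0.053 counting days).

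Range over the four season windows:

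| Arm, entry date | Alive during part of previous season | Mean share of season lived |
|---|---|---|
| 2A, 1 Sep | 100% | 74-85% |
| 2A, 1 Oct | 100% | 63-73% |
| 2A, 1 Nov | 83-100% | 50-58% |
| 2A, 1 Dec | 66-100% | 33-41% |
| 2B, 1 Jan | 33-55% | 12-17% |
| 2B, 1 Feb | 22-44% | 5-11% |
| 2B, 1 Mar | 11-33% | 1-6% |
| 2B, 15 Mar | 6-28% | 0.4-4% |

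**3. Possible number infected, before any screening.** Section 1.2 says: "It is estimated that 20% of children become infected with influenza yearly". The figure is for all children, not infants. Expected number = n × 0.20 × mean share.

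- 2A: 30 × 0.20 × 0.33 = 2.0, up to 30 × 0.20 × 0.85 = 5.1.
- 2B: 15 × 0.20 × 0.004 = 0.01, up to 15 × 0.20 × 0.17 = 0.5.
- At an assumed 5% rate, 2A: 30 × 0.05 × 0.33 = 0.5, up to 30 × 0.05 × 0.85 = 1.3.

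**4. Illustrative effect on Aim 2.** If k of 30 vaccine-arm infants respond like the infection arm, the difference becomes 0.40 × (1 − k/30), with SD held at 0.4. The last column removes those k infants instead and keeps the difference at 0.40.

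| k | Difference | Power, 30 v 15 | Power if the k are removed |
|---|---|---|---|
| 0 | 0.400 | 0.871 | 0.871 |
| 1 | 0.387 | 0.848 | 0.867 |
| 3 | 0.360 | 0.794 | 0.858 |
| 4 | 0.347 | 0.764 | 0.853 |

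**The case against.** The plan is not blind to the issue. Section 2.2 makes previously infected infants ineligible for 2A, subjects are identified by their primary care providers (section 4.1), and a complete medical history is taken at visit 1 with attention to eligibility (section 5.1). Recognised infections should therefore be screened out. Immunity is measured at entry and section 13.2 compares groups at each time point, so a group imbalance at baseline would be visible. This stands, and it limits the concern to unrecognised infection and to the lack of a rule for individual infants.

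Three stronger readings are tempting, and the documents do not support them.
- A reader might infer that only the vaccine arm is affected. Up to about half of 2B also overlaps the previous season under early entry dates, and the bar on earlier infection applies to 2A, not 2B. What is supported is an imbalance.
- A reader might take 2-5 of 30 as the number of enrolled 2A infants already infected. It is a count before screening, at a rate that is not infant-specific. The documents give no rate of unrecognised infection in early infancy.
- A reader might think that dropping 2A infants with a high visit 1 response is free of selection because the sample precedes vaccination. Section 13.2 tests visit 1 as one of three time points and plans a mixed model similar to that of Aim 1, which uses them all. For those analyses the exclusion would select on an outcome.

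Nor is bias towards no difference established for every endpoint. It follows only if the earlier-infected infants resemble the infection arm.

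**Conclusion.** The statement that the age range gives 2A a first influenza season is wrong as a matter of dates. Over the assumed windows, about 66-100% of 2A infants lived through part of the previous season (mean share 33-85%), against about 6-55% of 2B (mean share 0.4-17%). Earlier exposure is likely to be more common in 2A, but not exclusive to it.

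The eligibility condition in section 2.2 reduces the problem without closing it, because it names no means of ascertainment and the with/without analysis starts only after year 1. How many infants remain misclassified is unknown. The illustration of 1-4 infants, with power falling to 0.85-0.76, shows that a few would matter in an arm of 30; it is not an estimate. The dates claim rests on the stated ages and fall entry. The percentages also rest on uniform ages and assumed season dates.

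**What to change.** 1. In section 2.2 and the Figure 3 legend, replace the statement that the age range gives a first influenza season. Carry a criterion of no known prior influenza infection into section 3.2 for both 2A and 2B, and say how it is ascertained.
2. Extend the with/without analysis of section 5.5 to infection before entry. Repeat the day 10 and day 24 Aim 2 comparisons, and the 2A v 2B contrast in Aim 3, without 2A infants whose pre-vaccination visit 1 sample meets a positivity threshold for NP-specific response fixed in advance. Report this as a sensitivity analysis beside the full-set result. Do not apply the exclusion to the visit 1 comparison, or to a mixed model that has visit 1 as an outcome.
3. For 2B, whose first sample is taken during illness, use date of birth against the previous local season as the sensitivity classification.

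The cost is protocol wording and one extra analysis, using a draw and assays already planned. Power in the reduced set falls slightly: 0.858 for 27 v 15, against 0.871. The date-of-birth rule for 2B is cruder, since most infants it flags will not have been infected. If it removed 5 of 15, the plan's own table gives 0.761 for 30 v 10, so that result should be read as a check on robustness only. Infants with no visit 1 blood cannot be classified and should be counted.
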